### Background

In Hong Kong, over 3000 Anterior Cruciate Ligament Reconstructions (ACLR) are performed each year in order to restore knee function after an ACL injury. The ultimate goal of ACLR is to fulfil the return-to-play (RTP) criteria. Despite successful surgery and a demanding rehabilitation process, some athletes still fail to comply to RTP. And for those who achieve RTP, 23% of those who return to their sports would suffer a second ACL injury (1).

After ACL injury, the patients would undergo ACLR and post-operative rehabilitation. The rehabilitation gradually helps patients to regain mobility and strength, where most of the patients would be expected to RTP by 12 months. Despite comprehensive rehabilitation programs, a systematic review showed up to 35% of patients would fail to return to their preinjury level of play (2). Additionally, these patients were found to be 6 times more likely to sustain a second ACL injury within 24 months after ACLR than the healthy population (3).

Quadriceps muscle strength is one of the key determinants for a patient's successful return-to-play after ACLR, by which muscle size is a crucial factor of muscle strength. Quadriceps muscle atrophy is unavoidable after ACLR, while rehabilitation aids in recovering quadriceps muscle mass. However, despite good compliance, some patients respond poorly and fail to regain muscle mass. Quadriceps muscle atrophy can persist beyond the completion of the rehabilitation program in almost half the patients and the reason behind this is still unknown. This represents an area requiring significant investigation, as quadriceps muscle atrophy and weakness have been shown to be predictive of poor knee function, decreased performance in sports and increased risk of reinjury.

Graft-tunnel osteointegration is another key determinant for the successful outcome of ACLR. Tunnel widening and bone loss are common after ACLR which affect tendon graft fixation and subsequent osteointegration of the tendon graft. Transient loss of 5–10% of bone mineral density (BMD) around the knee has been found in our previous clinical study (19). The tunnel surface with decreased BMD can become less stable for tendon–bone integration due to increased bone resorption. A successful osteointegration of the tendon graft with normal BMD is vital for the rehabilitation of ACLR, as early stability of knee joint allows the patients to adopt more aggressive rehabilitation therapy and improve the outcomes of surgery. In addition, patients having a higher degree of knee pain were found to have a higher degree of bony sclerosis and overall subchondral osteopenia and were associated with more quadriceps atrophy. Thus, the bone microarchitectural evolution after ACLR is worth monitoring.

PEMF treatment can modulate mitochondrial activities for muscle gain. Molecular processes are sensitive to the magnetic flux at extremely low frequency (<300 Hz), which are equivalent to the Earth's natural magnetic resonance (Schumann resonance). Applying magnetic fields at these low frequencies in the form of magnetic pulses, like a timely push to swing. The pulsing action will enhance the human magnetosensitive processes, which include the electron transport chain in mitochondria, calmodulin signaling and ion channels. The affected signal transduction pathways further influence the downstream myogenesis (5). Therefore, a pulsed electromagnetic field (PEMF) may be a possible intervention to amplify molecular processes in favour of myogenesis (6).

PEMF therapy has been demonstrated to enhance cellular activity related to tissue healing (7), and offer beneficial effects such as pain relief, anti-inflammation and oedema resolution (8). Numerous variables in the delivery of PEMF signals (i.e., magnetic flux, frequencies, signal curve, polarity, etc) may have specific biological implications. Our group ([name]) showed that brief 10-minute exposure of 1.5mT amplitude of PEMF (Quantum Tx) on myoblast in-vitro could activate myogenesis. It is done so by stimulating the TRPC-1-mediated calcium entry and downstream factors as well as PGC-1 $\alpha$ , this mechanism (mentioned above) is similar to the myogenesis in exercise (4). PGC-1 $\alpha$  gene expression is influenced by every major signaling pathway that is activated in a contracting muscle (9). Additionally, it plays an important role in regulating the production and secretion of myokine. Therefore, PEMF exposure on top of regular exercise training, may promote the secretion of myokine and in turn promote muscle regeneration.

Our study will examine the efficacy of PEMF treatment introduced at the late postoperative period. It helps to set up the treatment regime for the PEMF device to impose myogenic effects, including exposure time per session, the number of treatment sessions and the duration of treatment. To our best knowledge, this proposed study aims to apply PEMF as an intervention for patients with myokine-mediated persistent quadriceps muscle atrophy after ACLR. In turn, it would be the first study to examine the correlation between PEMF and post-operative quadriceps muscle endurance, strength and mass. Apart from the quadriceps muscle, we will also examine the bone microarchitecture changes correlating to the PEMF treatment in the post-operative period.

## **Objective**

To conduct a double-blinded, randomized controlled trial to investigate the effects of PEMF treatment during the late postoperative period on quadriceps muscle strength and muscle weakness in ACL injured patients.

## **Hypothesis**

PEMF treatment is effective to reduce muscle weakness and promote a gain in quadriceps muscle strength for ACLR patients at the post-operation time points.

## **Setting**

The study will be carried out in the Department of Orthopaedics and Traumatology at Prince of Wales Hospital.

## **Subject recruitment**

The study protocol will comply with the Declaration of Helsinki and ICH-GCP. Subjects will be recruited from the Department of Orthopaedics and Traumatology of Prince Wales Hospital in Hong Kong and patients who can meet all the inclusion criteria will be invited to participate in two sessions of assessments.

A total of 80 post-ACLR subjects will be recruited and follow up for up to 12 months. They will undergo 1:1 randomization into two study arms:

1. PEMF treatment
2. Control (Sham treatment)

Inclusion criteria:

1. Aged 18-30 with a unilateral ACL injury
2. Sporting injury with a Tegner score of 7+
3. LSI for quadriceps strength <70% of the contralateral leg at 4 months post-op
4. Both knees without a history of injury/prior surgery

Exclusion criteria:

1. Ages smaller than 18 years old or greater than 30 years old
2. Any concomitant bone fracture, major meniscus injury or full-thickness chondral injuries requiring altered rehabilitation program post-op
3. Preoperative radiographic signs of arthritis
4. Metal implants that would cause interference on MRI
5. Non-HS graft for ACLR
6. Patient non-compliance to the rehabilitation program
7. Pregnancy or possibility of pregnancy

## **Outcome measures**

### Isokinetic muscle strength

The dynamometer (Biodex System 4, Biodex Medical Systems Inc., New York, USA) will be used. Subjects will perform a standardized warm-up exercise (5 min cycling) followed by the fatigue test. 5 repetitions at speed of 180°/s will be done first to familiarize the patient. Concentric/concentric contractions of knee extension/flexion will be tested at 180°/s for 30 repetitions. Subjects will be seated on the dynamometer chair with the hip flexed to 85°. The re-test reliability has been proven for this protocol (11). The relatively fast speed is chosen to perform the fatigue test since the fast-twitch muscle fibres are expected to fatigue faster at high speeds (12). Peak torque will be the single highest repetition value within the 30 repetitions (13). Muscle endurance could be reflected by fatigue test, where the trends for peak torque, work, and power will be examined. Fatigue Index (F.I.) will be used to calculate the percent decrease for each variable (13). Percent decrease =  $100 - [(last\ 5\ repetitions / first\ 5\ repetitions) \times 100]$ . For individuals that did not achieve their peak torque within the first 3 repetitions, a

second F.T. will be calculated as follows. Percent decrease =  $[100 - [(last\ 5\ repetitions / highest\ consecutive\ 5\ repetitions) \times 100]]$ , where the highest consecutive five repetitions will be determined by values attained from the repetitions immediately before and following, the single highest repetition value (13).

### Self-reported knee functions

The subjective functional outcome will be evaluated by the Lysholm knee scoring system, the International Knee Documentation Committee (IKDC) subjective scoring system, Tegner activity score and International Physical Activity Questionnaire (IPAQ) will be used.

- 1) Lysholm knee scoring system: Consists of eight items, total score ranging from 0 to 100 where higher scores indicate a better outcome with fewer symptoms or disability (14).
- 2) International Knee Documentation Committee (IKDC): Consisted of 10 questions on symptoms and activity ranging from 0 to 100 where 100 implies perfect knee function (15).
- 3) Tegner activity score: This is an activity level scaled from 1 (low activity) to 10 (high activity) (16).
- 4) International Physical Activity Questionnaire (IPAQ): The level of physical activities during the past 7 days will be evaluated with a validated Chinese version of the quantitative physical activity questionnaire (17).

### Muscle thickness

#### 1. Ultrasound Imaging

The Aixplorer® ultrasound system (SuperSonic Imagine, Aix-en-Provence, France) and a linear transducer probe with a bandwidth of 2-10 MHz (SuperLinear™ SL10-2, Vermon, Tours, France) were used to measure the muscle thickness of Vastus Medialis (VM), Vastus Lateralis (VL), and Rectus Femoris (RF) on both the injured and uninjured leg. Participants laid supine on a treatment table for the assessment. A measuring tape was used to locate VM, VL, RF and the patella by palpation, consequently marked with a pen for reference. For consistency and ease of comparison across patients, the locations measured and labelled as the three muscle groups follow the guidelines below. RF was marked at 1/2 of the distance from the anterior superior iliac spine (ASIS) to the superior pole of the patella, VM was located at 1/5 of the distance away from the midpoint of the medial patella border to the ASIS, and VL was noted at 1/3 of the distance from the midpoint of the lateral patella border to the ASIS. After locating the anatomical points, excess contact gel was applied on these points. The transducer probe was aligned in the transverse plane and moved along the entire muscle bundle to capture a view of the VM, VL and RF. The operator would position the probe into the sagittal plane to measure muscle thickness upon the marked anatomical points. Minimal pressure was applied on the limb to prevent the deformation of the muscle and the results would be derived from the average of three measurements.

#### 2. Magnetic Resonance Imaging (MRI)

Muscle volumes of quadriceps muscle are measured using a 1.5 or 3.0 Tesla MRI Scanner. Axial (3mm thick cut) T1W images are obtained from the anterior superior iliac spine (ASIS) to the patella. Quadriceps muscles were manually outlined in each axial slice. Muscle volume was calculated by summing all of the slice-multiplied by slice thickness. The quality of the muscle is assessed by analyzing the fat content of the muscle mass using a technique that has been reported by Reeder et al (15). Scans will be performed on both legs before the start of the PEMF treatment (4 months post-op) and only on the injured side repeated after the completion of the 8 weeks PEMF

treatment (6 months post-op). The uninjured side will be used as a reference for ‘normal volume’.

#### High-Resolution Peripheral Quantitative Computed Tomography Scans (HR-pQCT)

High-resolution peripheral quantitative computed tomography scans (HR-pQCT) using XtremeCT II (Scanco Medical AG®, Brüttisellen, Switzerland) provides an analysis of bone microarchitecture at human peripheral sites with high spatial resolution and low exposure to radiation. Bone mineral density (BMD, calibrated with hydroxyapatite standards) and finite element analysis of subchondral bone over the knee joint will be performed using the Scanco software. Scans will be performed on both legs before the start of the PEMF treatment (4 months post-op), and on the injured side after the completion of the PEMF treatment (6- and 12-months post-op). The uninjured side will be used as a reference for ‘normal’ bone condition.

#### Biomechanical analysis

The kinematics will be assessed by the skin marker-based motion analysis system (Vicon MX, Oxford, UK) with the lower-body marker setup followed the OSTRC standard protocol using 16-camera and 16 reflective skin markers. The kinetic variables including vertical and horizontal ground reaction force (GRF) and joint moments will be evaluated by a synchronized force plate (0.60 × 0.40 m, model OR6-7, AMTI, Watertown, Massachusetts) at the centre of the capture volume at 1000 Hz. From the SLH task, the knee kinematics in the landing phase is the key measurements including knee flexion angle at initial contact and the range of knee motions (flexion-extension, valgus-varus, external-internal rotation). The hip and ankle flexion angle at initial contact will also be recorded. The GRF will be normalized to body weight and moments will be normalized for body weight × limb length to make the comparison between subjects possible. All analyses for moments and angles were performed in the anatomical sagittal (XY) plane and are counted as positive for flexion angles and extension moments. The start of the rise in the vertical GRF will be used to determine initial ground contact. From the SLS task, the knee kinematics are the key measurements including the range of motions (flexion-extension, valgus-varus, external-internal rotation) and the frequency of the relative tibiofemoral angular displacements from the kinematics curve, which will be quantified by the number of peak appearance. The kinematic and kinetic variables were imported and calculated in the Matlab (The Mathworks Inc., Natick, Massachusetts, USA). A biomechanical analysis will be performed on all patients. At the same time, the motion will be videotaped by high-speed cameras.

#### Serum myokine evaluation

Phlebotomy (5ml) will be performed at pre-op, before PEMF treatment, at 4- and 8- weeks after commencement of treatment, and at post-op 12 months. The serum will be prepared by centrifugation and kept in a -80o freezer until use. Quantitative analysis for myokines and proteins related to muscle metabolism will be performed by Human Myokine Magnetic Bead Panel (Millipore) with Bioplex-200 bead-based suspension assay system (LKSIIHS core facilities), or enzyme-linked immunosorbent assay (ELISA). These include Brain-derived neurotrophic factor (BDNF), Fibroblast growth factor-21 (FGF-21), Interleukin-6 (IL-6), IL-15, Irisin, Myostatin (MSTN)/GDF8, Insulin-like growth factor 1 (IGF-1), FGF-2, IL-8, Follistatin, Musclin, Myonectin, Decorin, Meteorinlike, Osteopontin, Secreted protein acidic and rich in cysteine (SPARC), Klotho, Procollagen type III N-terminal peptide (P3NP), and C-terminal of troponin T1 (TNNT1).

#### Passive Knee laxity

To measure anterior-posterior knee laxity, the KT-1000 knee ligament arthrometer (MEDmetric Corp, San Diego, CA, USA) will be used. A manual force test will be applied until a 30lb sound signal is activated. Three trials will be performed. A side difference of 3 mm above is considered clinically relevant.

### Visual Analogue Scale

The subjective measurement for chronic and acute pain will be recorded by the Visual Analogue Scale (VAS). VAS consists of a 10-cm line which represents the continuum between “painless” and “worst pain from 0 cm to 10 cm. The subject will be asked to draw a mark of it before and after each PEMF treatment session.

## **Study design**

### Randomization and blinding

Participants will be randomized into 1:1 allocation. Blocked randomization will be undertaken based on the computer-generated allocation sequence, whereby 80 participants would be divided into blocks of 10 for 2 groups. Thereafter, the participants will use their key card to complete the assigned treatment regime, without knowing if the machine is delivering active or sham PEMF. Outcome assessors and trial administrators are blinded for the group allocation.

### Follow up time points

Subjects with a Tenger Score 7+ and with  $\geq 7\%$  of the deficit in total quadriceps volume on the involved leg compared with the uninvolved leg will be recruited into a randomized controlled trial. Baseline assessments including isokinetic quadriceps muscle strength, quadriceps muscle thickness, blood sampling for myokines measurement (5ml), biomechanical analysis, knee laxity and self-reported outcome with a questionnaire will be taken before commencement of treatment, and the same set of measurement will be monitored at 4- and 8- weeks after commencement of PEMF or sham treatment. MRI will be performed before PEMF and 8-weeks after the commencement of PEMF if possible. And at post-op 12 months, isokinetic quadriceps muscle strength, quadriceps muscle thickness, biomechanical analysis and questionnaire will be taken again. (Appendix 10)

### **Sample size calculation**

Quadriceps muscle endurance and strength will be employed as the primary outcome for sample size estimation. Based on our recent pilot result, the difference in extension strength between atrophy and non-atrophy group was 30 Nm (SD 60 Nm), providing an effect size 0.42. Hence, with effective size set at 0.42, the estimated sample size will be 64 (32 for each arm) will be able to achieve 90% confidence to detect the difference between the two groups with a significance level (alpha) of 0.05 using a two-sided sample test. With an inclusion of 25% dropout rate, we have modified the total sample size to be 80 (40 for each arm). Thus, 80 subjects will be recruited in total.

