### **Data processing and analysis**

The data obtained in the tests will be analyzed using Statistical Package for Social Science (SPSS) (IBM SPSS ver.26). For parametric data, a paired-sample t-test will be used. Wilcoxon signed-rank test will be used to analyze the data sets if they are non-parametric. The alpha level will be set at 0.05 for all statistical tests.

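### The primary outcome is named as endurance and strength together but sized on strength alone, and none of the three post-baseline visits is fixed as the deciding one

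*Protocol*

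**What the plan says.** **Variable.** The Sample size calculation says "Quadriceps muscle endurance and strength will be employed as the primary outcome for sample size estimation". Its next sentence gives one pilot figure only: "the difference in extension strength between atrophy and non-atrophy group was 30 Nm (SD 60 Nm"), converted to an effect size of 0.42 and tied to no visit. The Objective is to study the effect of PEMF "on quadriceps muscle strength and muscle weakness in ACL injured patients", and the Hypothesis likewise speaks of weakness and strength. Endurance appears in neither. The Background does list it, saying that "it would be the first study to examine the correlation between PEMF and post-operative quadriceps muscle endurance, strength and mass".

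**How each is measured.** Under Outcome measures, Isokinetic muscle strength, peak torque is the highest single repetition of 30 at 180°/s. Endurance is read from the same 30 repetitions through peak torque, work and power. A Fatigue Index is calculated for each, with a second formula for subjects who do not reach peak torque within the first three repetitions.

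**Visit.** Follow up time points says that after baseline "the same set of measurement will be monitored at 4- and 8- weeks after commencement of PEMF or sham treatment", and then "And at post-op 12 months, isokinetic quadriceps muscle strength, quadriceps muscle thickness, biomechanical analysis and questionnaire will be taken again". None of the three visits is marked as primary. The Hypothesis refers to post-operation time points in the plural.

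**Tests.** Data processing and analysis says "For parametric data, a paired-sample t-test will be used", with a signed-rank alternative, and "The alpha level will be set at 0.05 for all statistical tests".

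**The concern.** A confirmatory claim needs one variable, one time and one test, or a stated rule that combines several. Here two constructs share the primary label, only one of them is sized, and the time is left open. The error rate of the efficacy claim therefore depends on a choice that the protocol does not make. If that choice is made after the data are seen, a nominal 5% test no longer carries a 5% risk of a false claim. Even a reader who settles on strength still has three visits to choose from, each at 0.05.

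**Working it through.** **1. Which variable leads**

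| Place in the protocol | Strength | Endurance |
|---|---|---|
| Objective | yes | no |
| Hypothesis | yes | no |
| Sample size: naming sentence | yes | yes |
| Sample size: figures used | yes (30 Nm, SD 60 Nm) | none |
| Background, stated novelty | yes | yes (with muscle mass) |

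The weight of the text is on strength. The one sentence that names the primary outcome says otherwise. Endurance is also not a single variable: three quantities each have an index, and there are two formulas.

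**2. Which visit decides**

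The isokinetic test is done at 4 weeks, 8 weeks and 12 months post-op. The Objective, the Hypothesis, the sizing and the analysis section single out none of them.

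**3. The plan's own sizing figure**

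The plan gives 32 per arm for an effect size of 0.42, 90% (worded as confidence, read here as power) and two-sided 0.05. For two means:

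- n per arm = 2(1.960 + 1.282)² / 0.42² = 2 × 10.51 / 0.1764 ≈ 119.1, so 120 per arm. The stated 32 is not reproduced.
- Power at 32 per arm = Φ(0.42 × √(32/2) − 1.960) = Φ(−0.28) = 0.39; the noncentral t gives 0.38.
- With 30/60 = 0.50 as the effect size, power = Φ(0.50 × 4 − 1.960) = Φ(0.04) = 0.52; the noncentral t gives 0.50.

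The sample size is a separate matter. It is used here only because it limits which remedies are sensible.

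**4. Error rate if strength at any visit could carry the claim**

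Inputs: three visits (protocol), two-sided 0.05 (protocol), a PEMF-versus-sham test at each visit (assumed), no true effect, and a common correlation ρ between visits (assumed, because the protocol gives none). The quantity is P(at least one |Z| > 1.96) for three normal statistics. With independent visits it would be 1 − 0.95³ = 0.143. By simulation (1,000,000 draws):

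| ρ between visits | P(at least one p < 0.05) |
|---|---|
| 0.5 | 0.125 |
| 0.6 | 0.118 |
| 0.7 | 0.109 |
| 0.8 | 0.098 |
| 0.9 | 0.083 |

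A check with two-sample t-tests (40,000 simulated trials) at 32 and 40 per arm gives 0.123 and 0.126 for ρ = 0.5, and 0.082 and 0.083 for ρ = 0.9.

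**5. Error rate under other rules**

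- Strength at one fixed visit: 0.05.
- Strength required at all three visits: at most 0.05, since each test alone has 0.05.
- Strength and one endurance measure both required at one visit: 0.05 × 0.05 = 0.0025 at correlation 0, rising to 0.030 at correlation 0.9.

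**The case against.** **Detail may sit in the SAP.** Alpha allocation, testing order and the exact model are often left to an SAP, which is not at hand, so their absence is not held against the protocol. The 0.05 sentence is a routine statement of significance level and does not say that any significant result counts as success. This stands, and it is why the 8 to 13% is conditional. It does not cover the primary outcome itself, which the protocol states jointly and then sizes on one half.

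**Strength is implied.** This largely stands. A reader might infer that the primary variable is wholly undefined, but the Objective, the Hypothesis and the sizing figures do not support that. What remains is an inconsistent naming sentence and an open visit.

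**Larger error rates.** A reader might also count strength or endurance at any of three visits as success and arrive at about 12 to 23%. That needs an any-of-six rule that no section states. The top end also needs zero correlation between measures taken from the same 30 repetitions. It is not a fair size for this point.

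**Conjunctive readings.** Endurance and strength joined by *and* may mean that both must succeed, and plural time points may mean all of them. Neither reading inflates the error. Neither is stated, and the first still leaves the visit and the choice of Fatigue Index open.

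**Eight weeks is implied as end of treatment.** This is plausible, but no section says it, and strength is tested again at 12 months post-op.

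**The planned tests are paired.** The rates above describe between-arm tests, not the paired tests in the analysis section, which do not compare the arms. This is correct, and that choice of test is a defect of its own. It enters here only because a primary endpoint has no defined error rate until its between-arm test is named.

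**Conclusion.** The point holds in a limited form. The protocol contradicts itself on the primary outcome (two constructs named, one sized) and leaves the deciding visit open among three. That much is certain from the text. The consequence is conditional: about 8 to 13% instead of 5% if strength at any visit could support the claim, given visit correlations of 0.5 to 0.9, between-arm tests and no true effect. Under a single-visit rule the rate is 5%; under an all-visits rule, or a both-outcomes rule at one fixed visit, it does not exceed 5%. The documents do not show that the sponsor intends an any-success rule, so this is an endpoint definition to correct before unblinding, not evidence of an inflated analysis.

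**What to change.** - **Sample size calculation:** name one primary endpoint: injured-leg isokinetic quadriceps extension peak torque in Nm, as already defined under Isokinetic muscle strength, at one visit fixed before unblinding (for example 8 weeks), PEMF versus sham, two-sided 0.05. State whether the pilot's extension strength is this measure and, if not, what it was.
- **Hypothesis:** replace the plural time points with that single visit.
- **Data processing and analysis:** name the matching between-arm test, for example a linear model of the visit value on arm and pre-treatment value. Keep the paired tests for within-arm description. Limit the confirmatory 0.05 to the primary test.
- **Endurance and the other visits:** label them secondary. If endurance is to stay confirmatory, name one Fatigue Index variable and one formula and test it only after strength succeeds, which leaves the power for strength unchanged.

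Requiring both outcomes to succeed is not recommended. With the stated effect size and 32 per arm, power for strength alone is about 38%. If endurance had the same effect and were uncorrelated, the chance that both succeed would be about 0.38 × 0.38 = 14%.

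The cost is wording in three sections, with no new patients or measurements. The price is that endurance alone, or an effect seen only at another visit, can no longer carry the primary claim.

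### The between-arm strength comparison is planned on unadjusted torque, and the baseline torque measured in every patient is not used to sharpen it

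*Protocol*

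**What the plan says.** - **Primary outcome.** Under Sample size calculation: "Quadriceps muscle endurance and strength will be employed as the primary outcome for sample size estimation". No single variable, scale, leg or visit is attached to it.
- **Planning figures.** The same section reports that in the pilot "the difference in extension strength between atrophy and non-atrophy group was 30 Nm (SD 60 Nm", continues with "providing an effect size 0.42", says that "the estimated sample size will be 64 (32 for each arm", and claims to "achieve 90% confidence to detect the difference between the two groups" at a two-sided alpha of 0.05. No baseline value, change score or correlation enters.
- **Strength measure.** Under Isokinetic muscle strength: "Peak torque will be the single highest repetition value within the 30 repetitions". No scaling to body size, the other leg or baseline is mentioned.
- **Baseline data.** Follow up time points lists "Baseline assessments including isokinetic quadriceps muscle strength" before treatment starts. Strength is repeated at 4 and 8 weeks and at 12 months post-op.
- **Analysis.** Data processing and analysis names the paired t-test, or the Wilcoxon signed-rank test for non-parametric data. It names no test between the arms and no covariate.
- **Allocation.** Randomization and blinding describes 1:1 allocation in blocks of 10 and mentions no stratification.

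**The concern.** The trial is sized for a comparison of two arms, with the full between-patient spread of torque as the noise term. Part of that spread is stable difference between patients that was there before treatment. A pre-treatment measurement of the same quantity is usually the cheapest way to remove it, and this trial takes that measurement in everyone.

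The two sections that could use it do not. The sample size rests on an unadjusted SD. The named tests, if the pairs are pre-treatment and post-treatment values, use baseline only within a patient and never set one arm against the other. Replacing them with a plain two-sample test on follow-up torque would supply the missing comparison but leave the noise where it is.

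At stake is power in a small trial: a real difference could be missed because available information was not used. A covariate is also most credible when it is named before the data are seen.

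**Working it through.** **Inputs from the protocol:** difference 30 Nm, SD 60 Nm, stated effect size 0.42, 32 per arm, two-sided alpha 0.05.

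**Assumption:** the correlation r between baseline and follow-up torque of the involved leg is not given, so r = 0.3 to 0.8 is shown. Baseline and follow-up SDs are taken as equal.

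**1. The plan's own figure.** 30/60 = 0.50, not 0.42. An effect size of 0.42 with 30 Nm would need an SD of 30/0.42 = 71.4 Nm. Both values are carried forward. By the normal formula, a two-sided two-sample test with 90% power needs 120 per arm at 0.42 and 85 per arm at 0.50. The stated 32 per arm is not reproduced by either.

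**2. Unadjusted power, 32 per arm** (noncentral t, 62 degrees of freedom, noncentrality d·√(n/2)):
- d = 0.50: 0.50 × √16 = 2.00, power 50%.
- d = 0.42: 0.42 × √16 = 1.68, power 38%.

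**3. Baseline as covariate.** The residual SD becomes SD·√(1 − r²), so the effective effect size is d/√(1 − r²), with 61 degrees of freedom. Example at r = 0.6: √(1 − 0.36) = 0.8, so 60 Nm falls to 48 Nm, the effective d is 0.50/0.8 = 0.625, and the noncentrality is 0.625 × 4 = 2.50.

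| Assumed r | Adjusted SD (from 60 Nm) | Power, d = 0.50 | Power, d = 0.42 |
|---|---|---|---|
| unadjusted | 60.0 | 50% | 38% |
| 0.3 | 57.2 | 54% | 41% |
| 0.5 | 52.0 | 62% | 48% |
| 0.6 | 48.0 | 69% | 54% |
| 0.7 | 42.8 | 79% | 64% |
| 0.8 | 36.0 | 91% | 79% |

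**4. Change score instead of covariate.** Its SD is SD·√(2 − 2r). At r = 0.5 this is 60 × √1 = 60 Nm: no gain. At r = 0.3 it is 60 × √1.4 = 71.0 Nm, worse than ignoring baseline. So it matters that the baseline enters as a covariate.

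**5. Chance imbalance at baseline.** If the baseline SD is 60 Nm, the standard error of the baseline difference between arms is 60 × √(2/32) = 15 Nm. A gap above 30 Nm then has probability 4.6% (9.3% with SD 71.4 Nm). Only r times a gap carries into an unadjusted follow-up contrast. For a 15 Nm gap that is 15 × 0.3 = 4.5 Nm to 15 × 0.8 = 12 Nm.

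**The case against.** Several points on the other side stand.

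- **Covariates are often left to a statistical analysis plan, and sizing on an unadjusted SD is conservative if the analysis is adjusted.** True in general. Here, however, the protocol names its tests, and none of them is a baseline-adjusted comparison of the arms. The point is an improvement to a stated method.
- **Paired tests do use baseline.** They do, within a patient, if the pairs are pre and post. So it would be wrong to say that the analysis ignores baseline torque. What is missing is its use in the PEMF-versus-sham contrast.
- **The low starting powers come from the sample-size calculation.** Correct. The 50% and 38% are not caused by using unadjusted torque. Adjustment only recovers part of the shortfall.
- **The gain depends on an unknown correlation.** Correct. At r = 0.3 it is only 3 to 4 percentage points.

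A reader might also infer three stronger things that the protocol does not support:

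- **That the primary outcome is fixed as raw torque in Nm.** Nm appears only as the sizing scale, and the endurance part is a within-person percentage.
- **That the protocol contradicts itself on scaling.** Under Biomechanical analysis, moments are "normalized for body weight × limb length to make the comparison between subjects possible". That describes motion-analysis variables and sets no rule for the dynamometer. What scaling to body size would gain cannot be computed from the document.
- **That chance imbalance could pass for, or conceal, the 30 Nm effect as a bias.** Under randomisation, a valid between-arm test already includes this chance in its 5% error, and only a fraction r of any gap carries over.

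**Conclusion.** The point holds as one of efficiency. The protocol plans the strength comparison on unadjusted torque and states no analysis that uses the baseline value to sharpen the comparison between arms. With 32 per arm, the covariate would raise power from 50% to between 54% and 91% at 30 Nm with SD 60 Nm, and from 38% to between 41% and 79% at 0.42, for r from 0.3 to 0.8. The gain is material from about r = 0.5.

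This rests on an assumed r, on equal SDs at baseline and follow-up, and on the pilot SD applying to the patients enrolled. The pilot contrast was between atrophy and non-atrophy groups, so it says nothing direct about the effect of PEMF. Of the correlations shown, only r = 0.8 with SD 60 Nm reaches the intended 90% power. The adjustment therefore does not stand in for correcting the effect size and the sample size.

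**What to change.** - **Data processing and analysis:** state that the arms are compared on involved-leg extension peak torque at one chosen visit by ANCOVA, with treatment arm as factor and the patient's own baseline involved-leg peak torque as covariate.
- **Sample size calculation:** show the planning SD unadjusted and baseline-adjusted, SD·√(1 − r²), with r labelled as an assumption and a range given. Correct the effect size and the sample size separately.
- **Optional:** report torque also per kg body mass, or add body mass or sex as a covariate.

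The cost is wording and one degree of freedom (61 instead of 62 with 32 per arm). The baseline measurement is already scheduled, so no patients, visits or tests are added.
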